7.2.2. Exclusion Criteria

A patient who meets any of the following criteria will be excluded from the study:

1. Solid malignancy within 5 years of the projected enrollment date, or hematologic malignancy (including chronic lymphocytic leukemia [CLL]) at any time

Exception: Nonmelanoma skin cancer that has undergone potentially curative therapy, or in situ cervical carcinoma or in-situ prostate cancer with non-detectable prostate specific antigen or any other tumor that has been treated, and the patient is deemed to be in complete remission for at least 2 years prior to enrollment, and no additional therapy is required during the study period

2. Distant metastatic disease (M1), visceral and/or distant nodal
3. Prior radiation therapy for CSCC
4. Patients with a condition requiring corticosteroid therapy (>10 mg prednisone/day or equivalent) within 14 days of the first dose of study drug.

Exceptions: Physiologic replacement doses are allowed even if they are >10 mg of prednisone/day or equivalent, as long as they are not being administered for immunosuppressive intent. Inhaled or topical steroids are permitted, provided that they are not for treatment of an autoimmune disorder.

5. Patients with active, known, or suspected autoimmune disease that has required systemic therapy within 5 years of the projected enrollment date.

Exceptions: Patients with vitiligo, type I diabetes mellitus, and endocrinopathies (including hypothyroidism due to autoimmune thyroiditis) only requiring hormone replacement, childhood asthma that has resolved, or psoriasis that does not require systemic treatment are permitted.

6. History of interstitial lung disease (eg, idiopathic pulmonary fibrosis, organizing pneumonia) or active, noninfectious pneumonitis that required immune-suppressive doses of glucocorticoids to assist with management.
7. Uncontrolled infection with human immunodeficiency virus (HIV), hepatitis B or hepatitis C virus (HBV or HCV) infection; or diagnosis of immunodeficiency

Notes:

- Patients will be tested for HIV, HBV, and HCV at screening.
 - Patients with known HIV infection who have controlled infection (undetectable viral load [HIV RNA measured via polymerase chain reaction] and CD4 count above 350 either spontaneously or on a stable antiviral regimen) are permitted. For patients with controlled HIV infection, monitoring will be performed per local standards.
 - Patients with hepatitis B (HBsAg+) who have controlled infection (serum hepatitis B virus DNA measured via polymerase chain reaction that is below the limit of detection AND receiving anti-viral therapy for hepatitis B) are permitted. Patients with controlled infections must undergo periodic monitoring of HBV DNA. Patients must remain on anti-viral therapy for at least 6 months beyond the last dose of investigational study drug.
 - Patients who are hepatitis C virus antibody positive (HCV Ab+) who have controlled infection (undetectable HCV RNA by polymerase chain reaction either spontaneously or in response to a successful prior course of anti-HCV therapy) are permitted.
8. Active tuberculosis
 9. Myocardial infarction within 6 months of enrollment
 10. Any medical co-morbidity, physical examination finding, or metabolic dysfunction, or clinical laboratory abnormality that, in the opinion of the investigator, renders the patient unsuitable for participation in a clinical trial due to high safety risks and/or potential to affect interpretation of results of the study
 11. Documented allergic or acute hypersensitivity reaction attributed to antibody treatments.
 12. Prior treatment with anti-cancer systemic therapy within the last 3 years prior to projected enrollment date
 13. Any prior treatment with an anti-PD1/PD-L1 agent
 14. Has participated in a study of an investigational agent or an investigational device within 4 weeks of enrollment

15. Women with a positive serum chorionic gonadotropin HCG pregnancy test at the screening/baseline visit. Breastfeeding women are also excluded.
16. Women of childbearing potential* and sexually active men who are unwilling to practice highly effective contraception prior to the first dose of study therapy, during the study, and for at least 6 months after the last dose. Highly effective contraceptive measures include:
 - a. stable use of combined (estrogen and progestogen containing) hormonal contraception (oral, intravaginal, transdermal) or progestogen-only hormonal contraception (oral, injectable, implantable) associated with inhibition of ovulation initiated 2 or more menstrual cycles prior to screening
 - b. intrauterine device (IUD); intrauterine hormone-releasing system (IUS)
 - c. bilateral tubal ligation
 - d. vasectomized partner (provided that the male vasectomized partner is the sole sexual partner of the women of childbearing potential (WOCBP) study participant and that the vasectomized partner has obtained medical assessment of surgical success for the procedure)
 - e. and/or sexual abstinence^{† ‡}

* Women of childbearing potential are defined as women who are fertile following menarche until becoming postmenopausal, unless permanently sterile. Permanent sterilization methods include hysterectomy, bilateral salpingectomy, and bilateral oophorectomy.

A postmenopausal state is defined as no menses for 12 months without an alternative medical cause. A high follicle stimulating hormone (FSH) level in the postmenopausal range may be used to confirm a postmenopausal state in women not using hormonal contraception or hormonal replacement therapy. However, in the absence of 12 months of amenorrhea, a single FSH measurement is insufficient to determine the occurrence of a postmenopausal state. The above definitions are according to Clinical Trial Facilitation Group (CTFG) guidance. Pregnancy testing and contraception are not required for women with documented hysterectomy or tubal ligation.

[†] Sexual abstinence is considered a highly effective method only if defined as refraining from heterosexual intercourse during the entire period of risk associated with the study drugs. The reliability of sexual abstinence needs to be evaluated in relation to the duration of the clinical trial and the preferred and usual lifestyle of the patient.

[‡] Periodic abstinence (calendar, symptothermal, post-ovulation methods), withdrawal (coitus interruptus), spermicides only, and lactational amenorrhea method (LAM) are not acceptable methods of contraception. Female condom and male condom should not be used together.

17. Receipt of a live vaccine within 28 days of enrollment
18. Prior allogeneic stem cell transplantation, or autologous stem cell transplantation
19. Recipient of a solid organ transplant (other than corneal transplants)
20. Diagnosis of squamous cell carcinoma of unknown (or occult) primary

21. Patients who are committed to an institution by virtue of an order issued either by the judicial or the administrative authorities
22. Member of the clinical site study team or his/her immediate family, unless prior approval granted by the sponsor

7.3. Premature Withdrawal from the Study

The investigator and sponsor have the right to discontinue a patient from study drug or withdraw a patient from the study at any time.

Reasons for discontinuation of study drug or withdrawal from the study may include, but are not limited to:

- Patient withdrawal of consent at any time. A patient has the right to withdraw from the study at any time, for any reason, and without repercussion.
- Any medical condition that the investigator or sponsor determines may jeopardize the patient's safety if he or she continues in the study or continues treatment with study drug
- The investigator or sponsor determines it is in the best interest of the patient
- Patient noncompliance (eg, not complying with protocol required visits, assessments, and dosing instructions)
- Pregnancy

Every effort should be made to obtain information on patients who discontinue study drug but who do not withdraw consent to continue participation in the study by completing study assessments, as described in [Table 2](#) and [Table 3](#), and [Table 4](#).

7.4. Replacement of Patients

Patients prematurely discontinued from study/study drug will not be replaced.

8. STUDY TREATMENT

8.1. Investigational Treatment

Cemiplimab 350 mg IV infusion over 30 minutes (± 10 minutes) Q3W for up to 4 doses prior to surgery in Part 1 and (optional) up to 16 doses after surgery in Part 2. Cemiplimab 50 mg/mL will be supplied as a sterile liquid in single-use glass vials.

Instructions on dose preparation are provided in the pharmacy manual. Instructions on management of acute infusion reactions are provided in [Section 8.4.1](#).

There are no comparator treatments in this single arm study.

8.2. Dose Modification

Dose modification for an individual patient is not allowed. The management approach described in this protocol includes interruption of study drug and implementation of supportive measures.

8.3. Study Drug Discontinuation

This section provides guidance on management of AEs that are suspected to be related to study drug. The general approach to missed doses of study drug (eg, due to AEs) is “time marches on.” Missed doses of study drug will not be made up, unless ≤ 3 days from the scheduled date.

The investigator may choose to hold study drug at his/her clinical judgment regarding the safety of an individual patient, even if hold criteria are not formally met per protocol.

Adverse event severity is to be graded according to the National Cancer Institute Common Terminology Criteria for Adverse Events (NCI-CTCAE) version 5 (Section 10.5.1).

8.3.1. Reasons for Permanent Discontinuation of Study Drug

Study drug dosing will be permanently stopped in the event of:

- Evidence of pregnancy
- Serious or severe allergic reactions considered related to study drug
- Liver dysfunction consistent with Hy’s law (AST or ALT >5 x ULN and/or total bilirubin >3 x ULN)
- Any AE that meets criteria for permanent discontinuation described in 8.3 or Appendix 2 (or other unacceptable toxicity, including cemiplimab treatment delay ≥ 84 days due to toxicity in Part 2 of the study)
- Infusion reaction of \geq grade 3 severity during or directly following infusion of cemiplimab (Section 8.4.1)
- Patient noncompliance (eg, not complying with protocol required visits or assessments)
- Patient withdrawal of consent
- Progression of disease (neoadjuvant portion of the study)
- Disease recurrence (adjuvant portion of the study)
- Administration of radiation therapy (adjuvant portion of the study)
- The investigator or sponsor determining it is in the best interest of the patient

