8.3.2. Reasons for Temporary Discontinuation of Study Drug

Study drug may be temporarily stopped due to events that meet the criteria for treatment interruption described in Section 8.3.3 (and Appendix 2), Section 8.3.4 or Section 8.4.

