
Grade 4
 
 • Colitis: Life-threatening consequences; urgent intervention indicated • Diarrhea: Life-threatening consequences; urgent intervention indicated 	
Permanently discontinue study drug
	
 • Same as above • Consider lower GI endoscopy if symptoms are refractory despite the treatment or there is concern of new infections 	

RECOMMENDED ADVERSE EVENTS MANAGEMENT FOR IMMUNE-MEDIATED HEPATITIS

Immune-Mediated Hepatitis Grade*	Study Drug Management	Action & Supportive Care Guidelines	Diagnostic Considerations
Elevated ALT & AST >ULN to 3x ULN without elevated bilirubin	No change	
 Monitor liver function tests (LFT) more frequently until resolution to baseline values 	
All attempts should be made to rule out other causes such as metastatic disease, progressive liver disease, viral hepatitis, alternative drug toxicity, infectious causes and/or myositis.
 
* Please note that the gradings of immune-mediated hepatitis are not according to the CTCAE v5.

Elevated ALT & AST >3 to 10x ULN or if total bilirubin ≤3x ULN	Withhold study drug	
 Monitor liver function tests (LFT) more frequently until resolution to baseline values Consider appropriate consultation with hepatologist and liver biopsy to establish etiology of hepatic injury, if necessary Consider inpatient monitoring for patients with ALT/AST >8xULN and or elevated total bilirubin >3x ULN Treatment with systemic corticosteroids (1 to 2 mg/kg/day prednisone or equivalent) until resolution to ≤G1 and taper over at least 1 month If no improvement within 3 days after initiation of systemic steroids, consider additional immunosuppressive therapy ie, mycophenolate mofetil 0.5 to 1 g BID Several courses of steroid tapering may be necessary as symptoms may worsen when the steroid dose is decreased 	

RECOMMENDED ADVERSE EVENTS MANAGEMENT FOR ENDOCRINE EVENTS

Endocrine Events CTCAE v5 Grade	Study Drug Management	Action & Supportive Care Guidelines	Diagnostic Considerations

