
Severe or life threatening Severe: Elevated creatinine >3x baseline increase of ≥ 4.0 mg/dL Life-Threatening: Elevated creatinine >6x baseline Increase; dialysis indicated
	
Permanently discontinue study drug
	
 • Consultation with nephrologist in consideration of ultrasound and/or biopsy as appropriate • Consider inpatient care and monitor creatinine daily • Treatment with systemic corticosteroids (1 to 2 mg/kg/day prednisone or equivalent) until resolution to $\leq G1$ and taper over at least a month • If no improvement within 7 days after initiation of systemic steroids, consider additional immunosuppressive therapy ie, mycophenolate mofetil 0.5 to 1 g BID 	

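### Protocol 8.3.1 and the Appendix 2 hepatitis table differ on rechallenge when ALT and AST are both >3x to 10x ULN and at least one is >5x ULN, and no clause ranks them

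*Protocol*

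**What the plan says.** **Protocol 8.3.1** is mandatory: "Study drug dosing will be permanently stopped in the event of" a list of events. One item is liver dysfunction described as consistent with Hy's law and spelled out as "AST or ALT >5 x ULN and/or total bilirubin >3 x ULN". A separate item covers any AE that meets the permanent-discontinuation criteria of 8.3 or Appendix 2, including "cemiplimab treatment delay ≥ 84 days due to toxicity in Part 2 of the study". The liver item therefore stands on its own.

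**Protocol Appendix 2, immune-mediated hepatitis**, says to withhold study drug for "Elevated ALT & AST >3 to 10x ULN or if total bilirubin ≤3x ULN". The care column of that row adds "Consider inpatient monitoring for patients with ALT/AST >8xULN and or elevated total bilirubin >3x ULN", and asks for systemic corticosteroids "until resolution to ≤G1 and taper over at least 1 month".

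**Resumption.** Section 8.3.2 provides: "Study drug may be temporarily stopped due to events that meet the criteria for treatment interruption described in Section 8.3.3 (and Appendix 2"), 8.3.4 or 8.4. Section 8.3.3.2 says to consider resuming after a hold for an irAE of grade 3 or lower, once values are back to grade 1 or lower after a taper, typically to 10 mg/day of prednisone or less. Section 8.3.6 permits resumption if the criteria in 8.3.4 and Appendix 2 are met.

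**Precedence.** The only ranking sentence is in 8.3.4. It puts 8.3.4 and its Table 1 below 8.3.3, Appendix 2 and 8.4. It does not mention 8.3.1.

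**The concern.** The same liver values can lead a site to two different decisions about re-exposure, each supported by printed protocol text.

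The choice has consequences beyond the hold. Under 8.3.5 and 9.1.5.1, permanent discontinuation for toxicity in Part 1 sends the patient to surgery (if clinically appropriate) and makes the patient ineligible for adjuvant cemiplimab. A hold does neither by itself. In Part 2 the choice decides whether adjuvant dosing can continue. With about 20 sites, patients with identical laboratory results could be handled differently on a safety question.

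**Working it through.** The plan gives no figure to reproduce. The check has two parts: where the rules overlap, and how many doses depend on the choice.

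**1. Overlap**

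The withhold row is read narrowly, with both enzymes in its band.

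- 8.3.1 stop: the higher of ALT and AST is >5x ULN (or bilirubin is >3x ULN).
- Appendix 2 hold: ALT and AST are both >3x and up to 10x ULN.
- Both apply: both enzymes are >3x to 10x ULN and at least one is >5x ULN.

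Band each enzyme as up to 3x, >3x to 5x, >5x to 10x, and >10x ULN. Of the 4 × 4 = 16 cells, 3 conflict on enzymes alone:

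| ALT | AST |
|---|---|
| >5x to 10x | >5x to 10x |
| >5x to 10x | >3x to 5x |
| >3x to 5x | >5x to 10x |

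Example: ALT 7x, AST 4x, normal bilirubin is a permanent stop under 8.3.1 and a hold under Appendix 2. With both enzymes >3x to 5x and bilirubin no higher than 3x ULN, the rules agree. Taking the row's bilirubin alternative literally would only widen the overlap.

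The row's own care line confirms that it reaches past 5x: it covers ALT/AST >8x ULN and bilirubin >3x ULN. The bilirubin part also exceeds the row's own 3x limit. Withholding is not shorthand for stopping, because the severe renal row of Appendix 2 prints "Permanently discontinue study drug" where a permanent stop is meant.

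**2. Doses that depend on the choice**

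Inputs from the protocol:
- Part 1 doses are on days 1, 22, 43 and 64.
- Part 2 has 16 doses, at weeks 0, 3, …, 45.
- The dosing window is ±3 days, and missed doses are not made up (8.3, 9.1).
- The taper is at least 1 month, and the delay limit in Part 2 is 84 days.

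Assumptions:
- The event is found at the pre-dose laboratory tests on day D, and that dose is not given.
- r is the number of days to reach grade 1 or lower.
- A full taper takes 30 days.
- Gaps are counted on nominal dose days.

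*Part 2.* Doses left when dosing resumes at week w = (45 − w)/3 + 1.

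| Resumption | Condition | Found week 3 | Found week 15 | Found week 30 |
|---|---|---|---|---|
| D + 21 days | resumed within 21 + 3 = 24 days, taper not complete | w = 6: 14 | w = 18: 10 | w = 33: 5 |
| D + 42 days | r + 30 ≤ 42 + 3, so r ≤ 15 | w = 9: 13 | w = 21: 9 | w = 36: 4 |
| D + 63 days | r + 30 ≤ 63 + 3, so r is 16 to 36 | w = 12: 12 | w = 24: 8 | w = 39: 3 |
| D + 84 days or later | r > 36 | 0 | 0 | 0 |

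The D + 63 row holds only if the 84-day delay is counted from the missed dose (63 days). Counted from the last dose given, the gap is 63 + 21 = 84 days, and the entries become 0. In the last row the delay reaches 84 days on either count. Under 8.3.1 every entry is 0.

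*Part 1, with the full taper.* Ready day = D + r + 30, and the last dose window closes on day 64 + 3 = 67.
- Found day 22: 52 + r ≤ 67 gives r ≤ 15 and 1 dose, otherwise 0.
- Found day 43: 73 + r > 67, so 0.
- Found day 64: 0.

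*Part 1, resuming within 24 days.*
- Found day 22: days 43 and 64, so 2 doses.
- Found day 43: day 64, so 1 dose.

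*Carry-over to Part 2.* Because 9.1.5.1 bars adjuvant drug after permanent discontinuation for toxicity in Part 1, eligibility for up to 16 further doses is also at stake. The upper limit for an event found on day 22 is 2 + 16 = 18 doses.

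**The case against.** **The rules can be obeyed together.** Withholding does not order a restart. 8.3.1 is mandatory, while 8.3.2, 8.3.3.2 and 8.3.6 are permissive and Appendix 2 is guidance. Section 8.3.4 allows resumption only in line with the protocol's toxicity guidance, and the hepatitis row prints no restart criterion. A site that holds and then stops permanently breaches nothing. This makes the permanent stop the safer reading. It does not settle the matter: no sentence says 8.3.1 overrides an Appendix 2 hold, and 8.3.3.2 tells the site to consider resuming.

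**Hy's law may imply that enzymes and bilirubin must both be raised.** The label could be meant that way. The parenthesis says or between the enzymes and and/or before bilirubin, so read literally one enzyme is enough. If a conjunction was intended, 8.3.1 is worded wrongly.

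**Consultation limits divergence.** Section 9.2.3.5 requires consultation with the Medical/Study Director in some cases of persistent or unexplained abnormality. That helps, but it supplies no rule.

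**Stronger readings that the documents do not support.**
- A reader might infer that one rule lets dosing continue through marked liver injury. Neither does; both halt it at once.
- A reader might infer that 8.3.4 makes Appendix 2 prevail. Its sentence ranks only 8.3.4 and Table 1. A site extending its principle to 8.3.1 would be going beyond the text.
- A reader might infer that Appendix 2 says nothing above 10x ULN. No such row is visible, but tables may be broken in the text available, and this point does not depend on one.

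**Conclusion.** The inconsistency is real and of low severity. In the overlap region, 8.3.1 read literally requires a permanent stop, Appendix 2 says hold, and nothing ranks them. The conflict concerns rechallenge and what follows from it.

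The number of patients affected cannot be computed, because the documents give no hepatitis incidence. Per affected patient the stakes are upper limits. They assume an event of grade 3 or lower, a patient who chooses adjuvant drug where Part 2 is concerned, quick recovery and an investigator willing to rechallenge. A Part 1 patient on hold may still be refused adjuvant cemiplimab, because 3.2.3 limits it to patients without unacceptable toxicity in Part 1.

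It would be wrong to infer a threat to the primary result. A hold with a one-month taper loses most or all remaining Part 1 doses anyway, and no endpoint, analysis set or test changes. Little effect on pCR is expected.

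**What to change.** Give 8.3.1 and the Appendix 2 hepatitis table the same limits, and state in both that the mandatory stop in 8.3.1 governs where they differ.

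- Limit the withhold row to ALT and AST no higher than 5x ULN with bilirubin no higher than 3x ULN.
- Place the care line for ALT/AST >8x ULN and/or bilirubin >3x ULN under permanent discontinuation. If the source table already has such a row, align its limits; otherwise add one.
- If the sponsor meant Hy's law as a conjunction, correct 8.3.1 explicitly and keep a permanent-stop limit for isolated severe elevations. Merely replacing and/or with and would remove the 8.3.1 stop for isolated transaminases >10x ULN and isolated bilirubin >3x ULN, with no visible Appendix 2 row to take over.

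The cost is wording in two places at the next amendment and a clarification letter to sites. Data collection and analysis do not change. The downside is that some patients who recover will lose the chance of rechallenge.

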8.3.2. Reasons for Temporary Discontinuation of Study Drug

Study drug may be temporarily stopped due to events that meet the criteria for treatment interruption described in Section 8.3.3 (and Appendix 2), Section 8.3.4 or Section 8.4.

8.3.3. Immune-related Adverse Events and Study Drug Discontinuation

8.3.3.1. Identification of Immune-Related Adverse Events

Investigators must be extremely vigilant and be ready to intervene early in the management of irAEs, as the onset of symptoms of irAEs (eg, pneumonitis) may be subtle. An irAE can occur shortly after the first dose or several months after the last dose of treatment. All AEs of unknown

etiology associated with drug exposure should be evaluated to determine possible immune etiology. If an irAE is suspected, efforts should be made to rule out neoplastic, infectious, metabolic, toxin, or other etiologic causes prior to labeling an AE as an irAE.

Based on the emerging safety profile of cemiplimab and other antibodies targeting the PD-1/PD-L1 axis, working case definitions are provided in the Investigator's Brochure to help investigators distinguish irAEs from non-immune AEs commonly associated with PD-1 inhibition (Naidoo, 2015)(Weber, 2015). This is not exhaustive of all possible irAEs. Clinical presentations of less common irAEs, including neurologic, musculoskeletal, cardiac, renal, and ocular events (Hoffman, 2016)(Zimmer, 2016), should be reviewed in patients with concerning presentations.

The case definitions in the Investigator's Brochure have not been validated and are intended only as guidance for investigators to help distinguish irAEs from non-immune AEs. These definitions may evolve as clinical experience increases with cemiplimab and other antibodies targeting the PD-1/PD-L1 axis. Investigators' clinical judgment may include other factors when determining immune-relatedness.

Adverse events that meet the criteria for irAEs, as noted above in the Investigator's Brochure, should be reported as irAEs in the eCRF. If AEs corresponding to the common terms for irAEs are attributed as NOT related to cemiplimab by the investigator, additional information should be provided to substantiate an alternative attribution (eg, infectious diarrhea).

If not provided at the outset, this information may be requested by immediate edit checks or in subsequent queries. The sponsor may request additional information for any AE that is of a type known to be potentially immune-related (eg, rash, colitis, elevated transaminases, endocrine), but is deemed not an irAE by the investigator.

Any grade 3 or greater irAE should be reported as an adverse event of special interest (AESI) (Section 10.4.3).

